#### 9.1.3 Expectedness

The expectedness of an adverse event should be determined based upon existing safety information about the study drug using these explanations:

- *Unexpected*: An adverse event that is not listed in the Investigator's brochure or is not listed at the specificity or severity that has been observed.
- *Expected*: An adverse event that is listed in the Investigator's brochure at the specificity and severity that has been observed.
- *Not Applicable*: Any adverse event that is unrelated to the study drug.

Adverse events that are mentioned in the Investigator's brochure as occurring with a class of drugs or as anticipated from the pharmacological properties of the drug, but are not specifically mentioned as occurring with the particular drug under investigation are to be considered unexpected.

The investigator should initially classify the expectedness of an adverse event, but the final classification is subject to the Medical Monitor's determination.

## 9.2 Serious Adverse Events

An adverse event is considered serious if, in the view of either the investigator or sponsor, it results in any of the following outcomes:

- Death;
- A life-threatening adverse event;

Note: An adverse event is considered "life-threatening" if, in the view of either the investigator or sponsor, its occurrence places the patient or subject at immediate risk of death. It does not include an adverse event that, had it occurred in a more severe form, might have caused death.

- Inpatient hospitalization or prolongation of existing hospitalization;

Note: The term “inpatient hospitalization” refers to any inpatient admission (even if less than 24 hours). For chronic or long-term inpatients, inpatient admission includes transfer within the hospital to an acute/intensive care inpatient unit. Inpatient hospitalization does not include: emergency room visits; outpatient/same-day/ambulatory procedures; observation/short stay units; rehabilitation facilities; hospice facilities; nursing homes; or clinical research/phase 1 units.

Note: The term “prolongation of existing hospitalization” refers to any extension of an inpatient hospitalization beyond the stay anticipated or required for the reason for the initial admission as determined by the investigator or treating physician.

- A persistent or significant incapacity or substantial disruption of the ability to conduct normal life functions;

Note: A serious adverse event specifically related to visual threat would be interpreted as any potential impairment or damage to the subject’s eyes (e.g., hemorrhage, retinal detachment, central corneal ulcer or damage to the optic nerve).

- A congenital anomaly/birth defect.

Important medical events that may not result in death, are not life-threatening, or require hospitalization may be considered serious when, based upon appropriate medical judgment, they may jeopardize the patient or subject and may require medical or surgical intervention to prevent one of the outcomes listed in this definition.

### **9.3 Procedures for Reporting Adverse Events**

All adverse events and their outcomes must be reported to Ora, the study sponsor, and the IRB/IEC as required by the IRB/IEC, federal, state, or local regulations and governing health authorities and recorded on the appropriate eCRF.

#### **9.3.1 Reporting a Suspected Unexpected Adverse Reaction**

All adverse events that are ‘suspected’ and ‘unexpected’ are to be reported to Ora, the study sponsor and the IRB/IEC as required by the IRB/IEC, federal, state, or local regulations and governing health authorities.

#### **9.3.2 Reporting a Serious Adverse Event**

To ensure subject safety, all serious adverse events, regardless of relationship to the study drug, must be reported to the medical monitor within 24 hours of becoming aware of the event. All information relevant to the serious adverse event must be recorded on the appropriate case report forms. The investigator is obligated to pursue and obtain

information requested by Ora and/or the sponsor in addition to that information reported on the case report form. All subjects experiencing a serious adverse event must be followed up and the outcome reported.

In the event of a serious adverse event, the investigator must notify Ora and the sponsor within 24 hours; obtain and maintain in his/her files all pertinent medical records, information, and medical judgments from colleagues who assisted in the treatment and follow-up of the subject; provide Ora and the study sponsor with a complete case history, which includes a statement as to whether the event was or was not suspected to be related to the use of the study drug; Site should inform the IRB of the adverse event according to the IRB guidelines for reporting serious adverse events.

The Investigator will follow unresolved AEs to resolution until the subject is lost to follow-up or until the AE is otherwise classified. Resolution means the subject has returned to baseline state of health or the Investigator does not expect any further improvement or worsening of the AE (ongoing and stable). If the subject is lost to follow-up, the Investigator should make 3 reasonable attempts to contact the subject via telephone, and then a letter via certified mail.

Contact information for reporting Serious Adverse Events:

Name:	
Title:	Project Manager, Dry Eye
Company:	Ora, Inc.
Office [contact] [name]
Alternative [contact]
Office [contact]
Name:	
Title:	Medical Monitor
Office [contact]
Mobile [contact]
Office [contact]

#### **9.4 Procedures for Unmasking of Study Drug**

All subjects, investigators, and study personnel involved with the conduct of the study will be masked with regard to treatment assignments. When medically necessary, the investigator may need to determine what treatment arm has been assigned to a subject. When possible (i.e., in non-emergency situations), Ora and/or the study

sponsor should be notified before unmasking study drug. Subjects will also be unmasked for treatment-related SAEs or pregnancies in a similar manner. The Investigator should complete the appropriate forms (per the Safety Plan) and, when possible, discuss with Ora, the Medical Monitor, and TopiVert Pharma, Ltd whether unmasking is required. The Investigator can unmask study drug assigned to a subject using the black blinding laminate label that was placed in the Source Document from the subject's study drug kit by removing the protective plastic over it and then scratching it off. Documentation must be completed by the unmasking Investigator and filed in the subject's study file. The subject's study file must include documentation for the unmasking reason and date along with the signature and name of the person who unmasked the subject. A copy of the appropriate forms must be provided to Ora for the Trial Master File. Unmasked subjects will be discontinued from the study.

## **9.5 Type and Duration of the Follow-up of Subjects after Adverse Events**

The investigator will follow unresolved AEs to resolution until the subject is lost to follow-up or until the AE is otherwise classified. Resolution means the subject has returned to baseline state of health or the Investigator does not expect any further improvement or worsening of the AE. If the subject is lost to follow-up, the Investigator should make reasonable attempts to contact the subject via telephone, post, or certified mail. All follow-up will be documented in the subject's source document. Non-serious AEs identified on the last scheduled contact must be recorded on the AE eCRF with the status noted.

If the Investigator becomes aware of any new information regarding an existing SAE (i.e., resolution, change in condition, or new treatment), a new SAE/Unanticipated Report Form must be completed and faxed to Ora within 24 hours of the site's awareness of the new information. The original SAE form is not to be altered. The report should describe whether the event has resolved or continues and how the event was treated.

# **10 STATISTICAL HYPOTHESES AND METHODS OF ANALYSES**

## **10.1 Analysis Populations**

The following analysis populations will be considered:

- Modified Intent-to-Treat Population – The modified intent-to-treat (mITT) population includes all randomized subjects with one post baseline efficacy assessment. Efficacy analysis will be performed on the mITT population. Subjects in the mITT population will be analyzed as randomized.

- Per Protocol Population – The per protocol (PP) population includes subjects in the mITT population who do not have significant protocol deviations and who complete the study. Protocol deviations will be assessed prior to database lock and unmasking. Subjects in the PP population will be analyzed as treated.
- Safety Population – The safety population includes all subjects who have received at least one dose of the investigational product. Subjects in the Safety population will be analyzed as treated.

Summaries of the comfort data from the Comfort Assessment portion of the study will be performed on the safety population from that Assessment. The statistical analysis of safety data will be performed for the safety population, separately for the Comfort Assessment and the Safety and Efficacy Assessment of the study. The analysis of baseline and all efficacy data in the Safety and Efficacy Assessment of the study will be performed for the mITT population. The efficacy analyses may also be performed on the PP population as sensitivity analyses.

## 10.2 Statistical Hypotheses

Although the primary objectives of the study are to evaluate safety and tolerability, exploratory hypothesis testing will be performed for efficacy endpoints. For each efficacy endpoint and time point, the statistical hypotheses are as follows:

$H_0$ : There is no difference between the TOP1630 Ophthalmic Solution treatment group and placebo for the respective endpoint.

$H_1$ : There is a difference between the TOP1630 Ophthalmic Solution treatment group and placebo for the respective endpoint. A difference in favor of TOP1630 Ophthalmic Solutions will be considered a success for that endpoint.

## 10.3 Sample Size

The study is not powered to show statistical differences for any of the efficacy endpoints. The sample size was determined based on prior clinical trial experience in subjects with dry eye syndrome and is deemed to be robust sufficient to evaluate the safety and tolerability of TOP1630 Ophthalmic Solution in this population and to gather efficacy data that will aid in powering future clinical trials.

With a sample size of 60 subjects in the Safety and Efficacy Assessment, the study will have 79% probability of detecting AEs occurring at a rate of 5% or more in either treatment arm.

## 10.4 Statistical Analysis

### 10.4.1 General Considerations

The quantitative variables will be summarized using number of subjects (n), mean, median, standard deviation, minimum and maximum. The qualitative variables will be summarized using counts and percentages.

All summaries will be presented by treatment group. Summaries of data from the Comfort Assessment and Safety and Efficacy Assessment of the study will be summarized separately. Summaries will be provided for demographics, baseline medical history, concurrent therapies, and subject disposition.

[figure not shown]
For the purpose of summarization, medical history, concurrent therapies, and adverse events will be coded to MedDRA and WHO Drug dictionaries, as appropriate.

All efficacy analyses will be 2-sided at a significance level of 0.10.

### 10.4.2 Unit of Analysis

Safety endpoints will be analyzed for both eyes. For efficacy endpoints, the unit of analysis will be the “worst eye” as defined by the following:

#### 10.4.3 Missing Data

The efficacy analyses will be performed using observed data. In addition, for key endpoints of corneal staining and ocular discomfort, missing data will be imputed using the following methods:

- Using the last observation carried forward (LOCF) imputation method for missing values
- Using multiple imputation methods to account for missing data

#### 10.4.4 Multiplicity Consideration

There will be no adjustments for multiple endpoints or multiple treatment comparisons for this early phase, exploratory study.

#### 10.4.5 Safety Variables

Adverse events will be coded using the MedDRA dictionary.

Frequencies and percentages of subjects with treatment-emergent adverse events (TEAEs), serious TEAEs, and TEAEs causing premature discontinuation will be provided by treatment group. An AE is treatment emergent if it occurs or worsens after the first dose of study treatment. Furthermore, frequencies will be given of subjects with TEAEs by system organ class and preferred term; by system organ class, preferred term and maximal severity; by system organ class and preferred term for treatment-related AEs; by system organ class, preferred term for SAEs; and by system organ class, preferred term, and time of onset. Separate summaries will be provided for ocular specific and all AEs (including systemic).

Other safety endpoints including visual acuity, slit-lamp biomicroscopy, corneal sensitivity, undilated fundoscopy, intraocular pressure (non-contact), and vital signs will be summarized by treatment group, visit, and time point (where relevant) using descriptive statistics. Changes or shifts from baseline will also be summarized where appropriate. For assessments performed by eye, study eye and fellow eye will be summarized separately. In addition, shifts from baseline to worst on-treatment value for ocular safety assessments will be summarized.

#### 10.4.6 Tolerability Analyses

Drop Comfort Assessment results, completed by the subject, and physician assessment results will be summarized descriptively using counts and percentages with each response. In addition, scores will be summarized continuously using number of subjects (n), mean, median, standard deviation, minimum and maximum. Tolerability endpoints will be summarized for the Comfort Assessment and Safety and Efficacy

Assessment separately, as well as combining the like treatment arms from both study Assessments.

#### 10.4.7 Exploratory Efficacy Analyses

The continuous and ordinal secondary efficacy variables collected at each visit will be summarized descriptively (n, mean, standard deviation, median, minimum and maximum), and analyzed with two-sample t-tests comparing the active treatment groups to placebo. All visit-based data will be analyzed at each visit as well as change from baseline. A Wilcoxon rank sum test and an ANCOVA model adjusting for baseline will also be assessed where appropriate. Corneal fluorescein staining by region and total (Ora and NEI scales), lissamine green staining by region, tear film break-up time, conjunctival redness, unanesthetized Schirmer's test, ocular symptoms (Ora Calibra® scales and VAS), OSDI®, ocular discomfort and changes from baseline in these measures will be analyzed by visit and time point, where applicable (i.e., pre- and post-CAE®), using two-sample t-tests and Wilcoxon rank sum tests. Changes from baseline will also be analyzed using ANCOVA models adjusting for baseline values. For the measures of symptoms during CAE®, the ANCOVA models will also include the pre-CAE® measure as a covariate. Drop comfort will be summarized descriptively. Symptoms recorded on the daily diary will be analyzed using repeated measure ANCOVA models, where baseline scores are calculated as the average scores in the run-in period and post-baseline scores are calculated as weekly morning, afternoon, evening, and daily averages.

A full statistical analysis plan (SAP) will be finalized before database lock and unmasking.

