**8.1.4 Methods for Assignment to Treatment Groups:**

For the Comfort Assessment, prior to initiation of the study (at Visit 1a), each subject who qualifies for entry will be assigned a screening number. All screening numbers will be assigned in strict numerical sequence at a site and no numbers will be skipped or omitted. If all inclusion and exclusion criteria are met, each qualifying subject will then be assigned a randomization number at Visit 1a.

For the Safety and Efficacy Assessment, prior to initiation of study run-in (at Visit 1b), each subject who qualifies for entry will be assigned a screening number. All screening numbers will be assigned in strict numerical sequence at a site and no numbers will be skipped or omitted. If all inclusion and exclusion criteria are met at Visits 1b and 2b, each qualifying subject will then be assigned a randomization number at the end of Visit 2b.

The Sponsor, Investigator, study staff and subject will be masked to the subject's treatment arm during the randomization process and throughout the study.

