mmHg	Millimeters of Mercury
OD	Right Eye
OPI	Ocular Protection Index
OS	Left Eye
OSDI [®]	Ocular Surface Disease Index
OU	Both Eyes
OTC	Over-the-counter
PMNs	Polymorphonuclear Leucocytes
PP	Per Protocol
PT	Preferred Term
TID	Three Times a Day
SAE	Serious Adverse Event
SAP	Statistical Analysis Plan
SDC	Statistics and Data Corporation
SOC	System Organ Class
SOP	Standard Operating Procedure
TFBUT/TBUT	Tear Film Break-up Time
TEAE	Treatment Emergent Adverse Event
VA	Visual Acuity
VAS	Visual Analogue Scale
WHO	World Health Organization

1. Introduction

The purpose of this statistical analysis plan (SAP) is to describe the planned analyses and reporting for protocol TOP1630-TV-04, version 2.0 dated 20Jan2017.

This SAP is being written with due consideration of the recommendations outlined in the most recent International Conference on Harmonization (ICH) E9 Guideline entitled Guidance for Industry: Statistical Principles for Clinical Trials and the most recent ICH E3 Guideline, entitled Guidance for Industry: Structure and Content of Clinical Study Reports (CSR).

This SAP describes the data that will be analyzed and the subject characteristics, efficacy, and safety assessments that will be evaluated. This SAP provides details of the specific statistical methods that will be used. The statistical analysis methods presented in this document will supersede the statistical analysis methods described in the clinical protocol. If additional analyses are required to supplement the planned analyses described in this SAP they may be completed and will be identified in the CSR.

2. Study Objectives

The primary objective of this study is to compare the safety and tolerability of TOP1630 Ophthalmic Solution to placebo. The secondary objectives are to compare the efficacy of TOP1630 Ophthalmic Solution to placebo for the treatment of the signs and symptoms of dry eye syndrome.

3. Study Variables

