3.4 Statistical Hypotheses

The null and alternative hypotheses, based on the exploratory efficacy variables, are as follows:

H_0 : There is no difference between the TOP1630 Ophthalmic Solution treatment group and placebo for the respective endpoint.

H_1 : There is a difference between the TOP1630 Ophthalmic Solution treatment group and placebo for the respective endpoint. A difference in favor of TOP1630 Ophthalmic Solutions will be considered a success for that endpoint.

All hypothesis testing will be two-sided with a type I error rate (α) of 0.10. There will be no adjustments for multiple endpoints or multiple treatment comparisons for this early phase, exploratory study. Specifics of the statistical tests are provided in Section 14.

4. Study Design and Procedures

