9.3 Definition of Baseline

Baseline measures are defined as the last measure prior to the initiation of study treatment, usually at Visit 2b. If a measure is taken both pre-CAE® and post-CAE®, the baseline will be the time point matched value at Visit 2b. For measures from daily subject diaries, baseline is defined as the average of all available days' readings during the run-in period, where daily scores are first obtained by averaging the AM and PM scores for that day, as applicable. For changes from pre-CAE® to post-CAE® post first treatment, the change from pre-CAE® to post-CAE® at Visit 2b will be considered the baseline value. For purposes of analysis, only subjects with at least 5 days of data in the run-in period will be included in change from baseline summaries and analyses.

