14.6 Intraocular Pressure (IOP)

IOP will be measured at Visits 1b (post-CAE®) and 4b (post-CAE®). IOP will be summarized for both eyes combined by visit and treatment group using quantitative summary statistics. At Visit 4b, an IOP of ≥ 21 mmHg AND ≥ 10 mmHg over baseline (Visit 1b) will be considered an AE, and presented in the tabular summary. Results will be listed for both eyes at each visit.

15. Tolerability Analyses

Two tools will be used to assess drop comfort, each of which will be assessed at Visit 2b (Day 1) and Visit 3b (Day 15 ± 1), following the first dose of study drug.

subject will be used for this analysis. Drop comfort will be summarized using quantitative summary statistics. Statistical comparisons will employ two-sample *t*-tests as the primary method of analysis.

- Ora Calibra® Drop Comfort Questionnaire will be used to assess drop comfort

Drop Comfort Questionnaire responses will be summarized using qualitative summary statistics. Subjects with at least one negative response will also be summarized.

16. Exploratory Efficacy Analyses

The continuous and ordinal secondary efficacy variables collected at each visit will be summarized descriptively (n, mean, SD, median, minimum and maximum), and analyzed with two-sample *t*-tests comparing the active treatment groups to placebo. All visit-based data will be analyzed at each visit as well as change from baseline. A Wilcoxon rank sum test and an ANCOVA model adjusting for baseline will also be assessed where appropriate. Corneal fluorescein staining by region and total (Ora and NEI scales), lissamine green staining by region, TFBUT, conjunctival redness, unanesthetized Schirmer's test, ocular symptoms (Ora Calibra® scales and VAS), OSDI®, ocular discomfort and changes from baseline in these measures will be analyzed by visit and time point, where applicable (i.e., pre- and post-

[figure not shown]
CAE[®]), using two-sample *t*-tests and Wilcoxon rank sum tests. Changes from baseline will also be analyzed using ANCOVA models adjusting for baseline values. For the measures of symptoms during CAE[®], the ANCOVA models will also include the pre-CAE[®] measure as a covariate. Symptoms recorded on the daily diary will be analyzed using repeated measure ANCOVA models, where baseline scores are calculated as the average scores in the run-in period and post-baseline scores are calculated as weekly morning, afternoon, evening, and daily averages.

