16.2 Ocular Discomfort

Ocular discomfort will be assessed pre-CAE® and post-CAE® for both eyes at Visit 1b (Day -7 ± 1),

Ocular discomfort will be analyzed by visit and time point, where applicable (i.e., pre- and post-CAE® as well as the pre- to post-CAE change), using two-sample t-tests and Wilcoxon rank sum tests.

Change from baseline for ocular discomfort will be analyzed similarly to the change from baseline for corneal fluorescein staining. An ANCOVA model will be used to compare the change from baseline for ocular discomfort, as measured on the Ora Calibra® Ocular Discomfort scale, between TOP1630 Ophthalmic Solution and Placebo. The ANCOVA model will include treatment as the main effect term and baseline ocular discomfort at Day 1 (Visit 2b) as a covariate.

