16.12.2 ORA CALIBRA® OCULAR DISCOMFORT SCALE DURING CAE®

16.13 Ocular Protection Index (OPI) 2.0

Ocular protection index (OPI) will be assessed at Visits 2b and 4b, Pre-CAE®, on both eyes using the

The OPI and IBI will be summarized by visit using quantitative summary statistics. Change from baseline will also be summarized.

Statistical comparisons will employ two-sample *t*-tests as the primary method of analysis. An ANCOVA model adjusting for baseline will also be assessed as a sensitivity analysis.

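### Does the unnamed visit of the pre-CAE covariate in the during-CAE symptom ANCOVA bias the treatment comparison?

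*Protocol*

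**What the plan says.** Protocol 10.4.7 plans t-tests, Wilcoxon tests and ANCOVA of change from baseline for the efficacy measures. It then adds one rule for the challenge readings: "For the measures of symptoms during CAE®, the ANCOVA models will also include the pre-CAE® measure as a covariate". The general text of SAP section 16 carries the same rule: "the ANCOVA models will also include the pre-CAE[®] measure as a covariate". Neither sentence gives a visit.

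Four other places bear on it:

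- SAP section 1 sets the order of authority: "The statistical analysis methods presented in this document will supersede the statistical analysis methods described in the clinical protocol".
- SAP 9.3 defines baseline as the last measure before study treatment, usually at Visit 2b, and adds: "If a measure is taken both pre-CAE® and post-CAE®, the baseline will be the time point matched value at Visit 2b".
- SAP 16.2, on pre-CAE and post-CAE discomfort, names Visit 2b for its ANCOVA covariate.
- SAP 16.12.2, headed "ORA CALIBRA® OCULAR DISCOMFORT SCALE DURING CAE", is where the during-CAE method belongs. In the public copy only the heading can be read.

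**The concern.** Protocol 8.1.4 places randomization after the Visit 2b assessments: "each qualifying subject will then be assigned a randomization number at the end of Visit 2b". A Visit 2b pre-CAE score is therefore a true baseline covariate. A pre-CAE score from Visit 3b or 4b is not, because the subject has by then used study drug for about two or four weeks. That later score is also an outcome in its own right, since SAP 16.2 says: "Ocular discomfort will be analyzed by visit and time point, where applicable".

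The word *also* in the rule invites the same-visit reading, because baseline is already in the model. On that reading the treatment coefficient is the drug effect on during-CAE discomfort with pre-CAE discomfort held fixed. That differs from the plain between-group difference in the null hypothesis of SAP 3.4: "There is no difference between the TOP1630 Ophthalmic Solution treatment group and placebo for the respective endpoint". The ANCOVA and the t-test for Table 14.2.16 would then estimate different quantities. Protocol 10.3 says the efficacy data should help to power later trials, so a shrunken estimate could mislead planning.

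**Working it through.** **What the documents supply.** 30 subjects per arm, two-sided alpha 0.10, no efficacy power claim, and no SD, effect size or correlation for discomfort. The only stated probability, 79% for detecting an adverse event with a 5% rate, reproduces as 1 − 0.95^30 = 0.785. It has no bearing here. All inputs below are assumed, in SD units.

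**Step 1: what each model estimates.** Let Δd be the drug effect on during-CAE discomfort and Δp the effect on same-visit pre-CAE discomfort. Let β be the within-arm slope of during-CAE on same-visit pre-CAE discomfort, given Visit 2b during-CAE discomfort.

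- Visit 2b covariates only: coefficient = Δd.
- Same-visit pre-CAE covariate: coefficient = Δd − β × Δp.

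**Step 2: the slope.** With within-visit correlation w and cross-visit correlation c, β = (w − c²)/(1 − c²).

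- w = c = 0.5: β = 0.25/0.75 = 0.333.
- w = 0.7, c = 0.5: β = 0.45/0.75 = 0.600.

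**Step 3: the shift when Δd = 0.50.**

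- Δp = 0: 0.50 in both settings, so no shift.
- Δp = 0.25: 0.50 − 0.333 × 0.25 = 0.417, and 0.50 − 0.600 × 0.25 = 0.350. Simulated means were 0.420 and 0.347.
- Δp = 0.50: 0.50 − 0.333 × 0.50 = 0.333, and 0.50 − 0.600 × 0.50 = 0.200. Simulated means were 0.334 and 0.198.

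The direction depends on β. A second simulation used a correlation structure in which cross-measure correlations between visits are weaker. A zero slope left the effect at 0.50, and a slope of −0.152 raised it to about 0.57. With a slope of 0.4 and a drug that lowered only pre-CAE discomfort by 0.50, the same-visit model gave about 0.19 in favor of placebo. A positive slope is the expected case for one scale used twice on one day, but the documents do not report it.

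**Step 4: what insisting on Visit 2b would cost.** Take w = 0.8, c = 0.5 and Δp = 0.

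- Residual variance with both Visit 2b scores: 1 − 2 × 0.25/1.8 = 0.722. Noncentrality: 0.50/√(0.722 × 2/30) = 2.28.
- Residual variance with Visit 2b during-CAE and same-visit pre-CAE scores: 1 − (0.25 + 0.64 − 0.40)/0.75 = 0.347. Noncentrality: 0.50/√(0.347 × 2/30) = 3.29.

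Against a critical value of 1.67, the normal approximation gives about 73% and 95% power; simulation gave 72% and 94%. If instead Δp equals Δd, the same-visit model falls to 21% while the Visit 2b model stays at 72%. Neither choice is better throughout.

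**Step 5: which reading do the texts support?** SAP 9.3 and 16.2 both point to Visit 2b, and *also* fits a Visit 2b pre-CAE score added to a Visit 2b during-CAE score. It fits the same-visit score too. The visible text does not decide, and the section that would decide cannot be read.

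**The case for a change.** The case for a change is that the algebra is right, the visit is not named in either general sentence, and naming it would cost one sentence per document with data already collected. SAP 16.2 shows that the authors could be explicit. Fixing the visit before unmasking would also rule out a later choice between two estimates. All of this stands as a reason to read SAP 16.12.2.

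It does not establish a fault, for four reasons.

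- The general sentence is a summary. The detail belongs in 16.12.2, whose body is not visible. The SAP abbreviation list defines terms such as AICc, compound symmetry and least squares that I cannot find used in the visible text. That suggests model detail was removed, though not from which section.
- A same-visit model is a reasonable question for a challenge design: how much discomfort the CAE provokes given the state on entry. The plan declares an interest of this kind, with a baseline rule for pre-to-post change in SAP 9.3 and Figures 14.2.3.3 and 14.2.3.4.
- Eligibility requires discomfort of at least 3 at two consecutive readings during the Visit 2b challenge. That narrows the range of the Visit 2b score and could weaken its correlation with later visits. At assumed c = 0.3, w = 0.7 and Δp = 0, power is about 65% with Visit 2b covariates against 86% with the same-visit score.
- The planning risk is limited. Means and SDs by arm and two-sample t-tests are planned for the visit-based measures. The visible endpoint sections from SAP 16.4 onward that state their tests for visit-based measures make the t-test the primary method. Someone sizing a later trial has unadjusted inputs.

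**Conclusion.** No change to the plan follows. The visible wording leaves one covariate's visit open. The governing section may settle it, and an analyst who follows SAP 9.3 has a sensible default in Visit 2b.

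A smaller estimate arises only if three conditions hold together: the same-visit score is used, the drug also lowers pre-CAE discomfort, and the within-arm slope is positive. Under the assumed correlations of 0.5 to 0.7 and a half-size pre-CAE effect, about 17% to 30% of a 0.50 SD effect would be removed (0.083/0.50 and 0.150/0.50). With no pre-CAE effect nothing is removed. These figures illustrate the mechanism only.

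Even then, the result is a legitimate but different quantity in one exploratory ANCOVA, with no multiplicity claim and no efficacy power attached to it. The t-tests and Wilcoxon tests do not use the covariate. Requiring Visit 2b covariates would protect the total effect but could lose about 22 points of power (94% against 72%) when the drug has no pre-CAE effect, so the choice is a fair trade-off.
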